## **2. Introduction**

### **2.1. Study Rationale**

#### **Part A**

Remote assessments of individuals with AD via telemedicine have the potential to reduce burdens associated with clinical care and research participation. Research comparing clinical interviewing conducted through video conferencing and traditional on-site conditions has suggested generally good agreement in a variety of conditions, including dementia and cognitive impairment of various causes. However, limited data is available on the validity of remote web-based assessment of cognitive and functional measures typically implemented in AD research studies. Therefore, the aim of Study I5T-MC-AACH (AACH) Part A is to evaluate the validity of remote (at-home) video assessments of cognitive and functional measures.

Study AACH Part A is a multicenter, randomized, multiple crossover study to validate remote assessment of cognitive and functional scales. Participants will be assessed remotely (through videoconferencing) as well as on-site.

#### **Part B**

Part B is a multicenter, open-label, study of donanemab treatment for participants with symptomatic AD and naive to donanemab.

Study AACH Part B will provide additional safety and clinical information as an open-label study. Participants from a sponsor-approved originating donanemab study who were assigned placebo will receive donanemab in the single open-label arm.

#### **Part C**

Those who received donanemab in an originating study may participate in a single imaging and cognitive/functional assessment visit.

Study AACH Part C will assess the long-term effect of donanemab on PET imaging biomarkers, cognition, and functioning in participants who have not received IP for at least 52 weeks.

### **2.2. Background**

#### **2.2.1. Disease State**

AD is an age-related neurodegenerative disorder characterized by progressive decline in cognitive function and the ability to perform activities of daily living. The amyloid hypothesis of AD postulates that the accumulation of A $\beta$  is an early and necessary event in the pathogenesis of AD. This hypothesis suggests that interventions that slow the accumulation of A $\beta$  plaque in the brain or increase clearance of A $\beta$  may be able to slow the progression of the AD clinical syndrome. Another hallmark neuropathological lesion of AD is comprised of intraneuronal, neurofibrillary tangles consisting of tau proteins, which spread through the brain and mark disease progression (Braak and Braak 1996). The relationship between these 2 pathologies is still unclear, although the presence of both is necessary for the diagnosis of definite AD.

Converging evidence from both genetic at-risk and age at-risk cohorts suggests that the pathophysiological process of AD begins well more than a decade before the clinical stage now recognized as AD dementia, and that neurodegeneration is already apparent on MRI by the stage of MCI. Like many disorders, AD occurs on a continuum from asymptomatic (preclinical) to MCI, and then to dementia in mild, moderate, and severe stages. Recent clinical trial results in mild-to-moderate AD dementia, as well as evidence from transgenic animal experiments, suggest that treating AD during the earlier stages could have the greatest potential benefit on the disease and inhibiting progression, particularly when considering therapies targeted at A $\beta$  reduction (Doody et al. 2014; Fleisher et al. 2015; Siemers et al. 2016).

### **2.2.2. Video Assessment**

VTC in healthcare settings is common and is used to carry out cognitive assessments, to conduct psychiatric interviews and consultations, and to help with the management of chronic conditions (Cullum et al. 2014; Ignatowicz et al. 2019). Research comparing clinical interviewing conducted through video conferencing and traditional on-site conditions indicates generally good agreement in a variety of conditions, including dementia and cognitive impairment of various causes (Castanho et al. 2017).

A recent systematic review and meta-analysis assessed the effect of VTC administration on adult cognitive tests and investigated whether the scores acquired during a VTC administration were different from those acquired during on-site administration (Bearly 2017). The review concluded that studies including participants with a mean age of 65 to 75, as well as studies that utilized a high-speed network connection, indicated consistent performance across VTC and on-site conditions (studies with slower connections were more variable). Furthermore, subgroup analyses indicated that VTC scores for untimed tasks and those allowing for repetition fell 1/10th of a standard deviation below on-site scores. Test-specific analyses indicated that verbally mediated tasks were not affected by VTC administration but tasks with a motor component yielded more variable data.

With specific regard to instruments that are often used in AD clinical trials, the feasibility of the MMSE by VTC in an older population with dementia has been investigated by several authors (Ciemins et al. 2009; Cullum et al. 2014; Castanho et al 2017) and no differences were reported between video and on-site administrations.

VTC of the ADAS-Cog13 has not been investigated as often as the MMSE. Results from 2 studies show no difference in baseline and follow-up scores of the ADAS-Cog13 between on-site and VTC testing (Carotenuto et al. 2018; Yoshida et al. 2020). One of these studies reported that in patients with more pronounced cognitive deficits (MMSE <17), the assessment via VTC overestimated the cognitive impairment (Carotenuto et al. 2018).

There are a couple notable limitations of these studies: the remote assessment did not take place at the participant's home or other designated external environment, but rather, on-site, with the participant being located in a different room from the test administrator. Also, in most studies described above, a technician was available to set up the audiovisual and VTC hardware. As such, remote administration in a real-world (at-home) setting needs to be further investigated.

Further, test scores are reliable if the scale is administered in accordance with how that scale has been validated. Any modification to an assessment-validated version can invalidate test scores.

To allow for remote administration, certain scale elements need to be modified as they require physical interaction between study partner and rater for its administration. How these modifications have been operationalized (and thus, to what extent validity has been established) is not clear.

Therefore, this study aims to evaluate the reliability of remote administration, compared to on-site administration, of the specific cognitive and functional measures described.

### **2.2.3. Donanemab**

Donanemab is an antibody directed at the pyroglutamate modification of the third amino acid of A $\beta$  (N3pG A $\beta$ ) epitope that is present only in brain amyloid plaques. It is being studied for the treatment of AD. The mechanism of action of donanemab antibody is to target and remove deposited amyloid plaque, a key pathological hallmark of AD, via microglial-mediated clearance.

#### **2.2.3.1. Donanemab Clinical Studies**

The first human dose study of donanemab was Study I5T-MC-AACC (AACC). Study AACC was a Phase 1, double-blind, randomized within cohort, placebo-controlled, parallel-group, single-dose followed by multiple-dose, dose-escalation study in patients with MCI due to AD or mild-to-moderate AD to assess the safety, tolerability, PD, and PK of single and multiple IV doses of donanemab. After single-dose administration from 0.1 mg/kg to 3.0 mg/kg, the mean terminal elimination half-life was approximately 4 days, increasing to approximately 10 days (243 hours) at the 10-mg/kg dose level. The PK of a single dose of 1.0 mg/kg IV of donanemab in young, healthy subjects was indistinguishable from the PK in AD patients at the same dose level.

In Study AACC, florbetapir F 18 scans were performed at baseline and after the last multiple-ascending dose, separated by approximately 7 months, to assess the PD effects of donanemab. The change from baseline in grey matter Standardized Uptake Value ratio with cerebellum as a reference region was compared across dose cohorts. There was a highly significant reduction from baseline in cerebral amyloid by PET at the highest dose, 10 mg/kg ( $p < .0002$ ). The analysis showed consistent reduction in cortical amyloid among the patients who received 3 to 5 doses of 10 mg/kg of donanemab. The mean observed reduction in florbetapir F 18 PET signal corresponds to a mean 50% reduction in total brain fibrillar amyloid. Meaningful target engagement (amyloid reduction) was likely not achieved at doses smaller than or equal to 3 mg/kg IV Q4W because of the rapid elimination of donanemab and the lack of sustained exposure.

Study I5T-MC-AACD (AACD) is a Phase 1b single- and multiple-dose study to assess the safety, tolerability, PK, and PD of IV donanemab in patients with MCI due to AD or mild-to-moderate AD. Study AACD has completed clinical activity and patients are no longer being dosed, but the study has not completed database lock. It is evaluating 61 patients in 7 treatment groups receiving single-dose, Q2W or Q4W dosing of either 10 mg/kg, 20 mg/kg, or 40 mg/kg of donanemab. Treatment durations being assessed include single-dose, 6-month dosing Q2W, or up to 72 weeks of Q4W dosing. Safety, PK, and PD data from this ongoing study are used to inform further development of donanemab.

Study I5T-MC-AACG (AACG) is an ongoing Phase 2, double-blind, placebo-controlled study to evaluate the safety and efficacy of donanemab in patients with early symptomatic AD.

Study AACG is evaluating approximately 272 patients randomized to donanemab (700 mg Q4W for 3 doses, then 1400 mg Q4W) or placebo.

Study I5T-MC-AACI (AACI) is an ongoing Phase 2, double-blind, placebo-controlled study to evaluate the safety and efficacy of donanemab in patients with early symptomatic AD.

Study AACI is evaluating approximately 500 patients randomized to donanemab (700 mg IV Q4W for 3 doses, then 1400 mg IV Q4W) or placebo.

See the IB for detailed nonclinical, safety, and PK information regarding donanemab.

### **2.3. Benefit/Risk Assessment**

More detailed information about the known and expected benefits and risks and reasonably expected AEs of donanemab may be found in the IB.

### 3. Objectives and Endpoints

Objectives	Endpoints
Primary	
Part A To evaluate the reliability of VTC compared with on-site administered cognitive and functional measures	The intraclass correlation between VTC and on-site assessment for PAIR 1 for 
 
• ADAS-Cog13
 
• ADCS-ADL
 
• MMSE
 
• CDR-SB
 

Part B To evaluate safety and tolerability of donanemab	Standard safety assessments in Part B: 
 
• Spontaneously reported AEs
 
• Clinical laboratory tests
 
• Vital sign and body weight measurements
 
• 12-lead ECGs
 
• Physical and neurological examinations
 
 MRI (ARIA and emergent radiological findings) Infusion-related reactions C-SSRS
Secondary	
To assess the effect of donanemab on clinical progression in participants with symptomatic AD	Change from baseline up to Week 72 as measured in Part B by: 
 
• MMSE score
 
• ADAS-Cog13 score
 
• iADRS score
 
• ADCS-iADL score
 
• CDR-SB
 

To assess the effect of donanemab on brain amyloid deposition	Change in brain amyloid plaque deposition from baseline at Week 36 of Part B as measured by florbetapir F 18 PET scan
To assess the effect of donanemab on brain region volumes	Change in volumetric MRI measures from baseline to Week 72 in Part B
To assess peripheral PK and presence of anti-donanemab antibodies	PK of donanemab in Part B. ADAs against donanemab in Part B including 
 
• treatment-emergent ADAs
 
• neutralizing antibodies
 

Tertiary/Exploratory	
To assess long-term effect of donanemab on brain amyloid deposition, brain tau deposition, blood-based biomarkers, and clinical progression of AD in participants who received donanemab in the originating study	Change in the following endpoints from baseline in the originating study through $\geq 52$ weeks after the participant's last double-blind visit in the originating study, using Part C assessments: 
 
• Amyloid plaque deposition as measured by florbetapir F 18 PET scan
 
• Tau deposition as measured by flortaucipir F 18 PET scan
 
• NfL
 
• P-tau
 
• A<math>\beta</math>
 
• MMSE score
 
• ADAS-Cog13 score
 
• iADRS score
 
• ADCS-iADL score
 
• CDR-SB
 

To assess the effect of donanemab on blood-based biomarkers	Change from baseline to Week 72 in the following blood-based biomarkers in Part B: 
 
• NfL
 
• P-tau
 
• A<math>\beta</math>
 

To evaluate the reliability of VTC compared with on-site administered cognitive and functional measures	
The intraclass correlation between VTC and on-site assessment for PAIR 2 and PAIR 3 compared with intraclass correlation of PAIR 1 for
 
 
• ADAS-Cog13
 
• ADCS-ADL
 
• MMSE
 
• CDR-SB
 

To assess clinical progression as measured by VTC versus F2F-administered cognitive and functional measures	
Change from V602 to V608 as measured by
 
 
• ADAS-Cog13
 
• ADCS-ADL
 
• MMSE
 
• CDR-SB
 

Abbreviations: A $\beta$  = amyloid beta; AD = Alzheimer's disease; ADA = antidrug antibody; ADAS-Cog13 = Alzheimer's Disease Assessment Scale – Cognitive subscale; ADCS-ADL = Alzheimer's Disease Cooperative Study – Activities of Daily Living Inventory; ADCS-iADL = Alzheimer's Disease Cooperative Study – instrumental Activities of Daily Living; AE = adverse event; ARIA = amyloid-related imaging abnormality; CDR-SB = Clinical Dementia Rating Scale – Sum of Boxes; C-SSRS = Columbia Suicide Severity Rating Scale; ECG = electrocardiogram; F2F = face to face; iADRS = integrated Alzheimer's Disease Rating Scale; MMSE = Mini Mental State Examination; MRI = magnetic resonance imaging; NfL = neurofilament light chain; PET = positron emission tomography; PK = pharmacokinetics; P-tau = phosphorylated tau; V = visit; VTC = video teleconference.

## 4. Study Design

### 4.1. Overall Design

#### Part A:

The video validation period is a multiple crossover design with participants alternating between in-clinic assessments and at-home assessments of cognitive and functional scales over a minimum of 1 and a maximum of 3 crossovers. Total time in Part A can vary from a minimum of 4 weeks (1 crossover [1 PAIR]) to a maximum of 24 weeks (3 crossovers [3 PAIRS]). Participants do not receive study IP during the video validation period. Participants are randomized 1:1 in regards to order of in-clinic or at-home for the first assessment, either:

- Group 1: Cognitive/functional scale assessment at the study site (on-site), followed by an at-home assessment (VTC; video teleconference), or
- Group 2: Cognitive/functional scale assessment at home (VTC), followed by assessment on-site.

#### Part B:

Part B is a multicenter, open-label, follow-on study of donanemab in participants with symptomatic AD. Participants who received placebo in the originating trial receive:

- donanemab 700 mg IV Q4W for 3 doses, then
- donanemab 1400 mg IV Q4W for up to 36 weeks in Part B.

Participants may receive donanemab through Week 36 or Week 48. Criteria for scheduled dose discontinuation at 36 weeks are defined by the sponsor and may be based on results of the participant's florbetapir F 18 PET scan at Week 36 or results from external studies such as Study AACG.

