Visit Interval Tolerance (days)		-		-7 to +10	±7	±7	±7	±7	±7	±7	±7	±7	±7	±7	±7	±7	±7	±7	±7	±7			
PK sample (predose)				X	X		X		X			X			X								Do not collect if the last IP infusion was >6 months prior to the scheduled visit. Predose collections may be collected from the IV site prior to the infusion.  Random PK sample collected for participants who do not receive dose at V13.
PK sample (postdose)			X			X		X															Do not collect if the last IP infusion was >6 months prior to the scheduled visit. Collect within 30 minutes of IP administration. Collect from the arm that IP was not administered through.
PK sample (random)																X	X	X	X		X		Do not collect if the last IP infusion was >6 months prior to the scheduled visit.
Immunogenicity (ADA) samples			X	X	X		X		X			X			X	X	X	X	X		X		

		Part B: Open-Label																	Part B: Follow-Up, UV, ED				Comments	
		1	2	3	4	5	6	7	8	9	10	11 c	12 c	13 c	14 c	15	801 d	802 d	UV	ED				
Visit Number	UP b	1	2	3	4	5	6	7	8	9	10	11 c	12 c	13 c	14 c	15	801 d	802 d	UV	ED	ED only if participant has completed V1 and received IP in Part B.			
Weeks Relative to Baseline (V1)		0	4	8	12	16	20	24	28	32	36	40	44	48	60	72	84	96	997		Procedures for some visits may take more than 1 day.			
Visit Interval Tolerance (days)		—	-7 to +10	±7	±7	±7	±7	±7	±7	±7	±7	±7	±7	±7	±7	±7	±7	±7	±7					
Stored Samples																								
Exploratory biomarker samples			X			X			X			X				X			X		X		X	Collect unless not allowed or unfeasible due to local regulations.
Randomization and Dosing																								
Contact IWRS - dispensation of IP		X	X	X	X	X	X	X	X	X	X	X	X	X										Only contact IWRS at V11, V12, and V13 for participants receiving IP for 48 weeks.
Administer IP		X	X	X	X	X	X	X	X	X	X	X	X	X										Administered by IV at study site. The participant should be observed for a minimum of 60 minutes following the end of each infusion. Only administer IP at V11, V12, and V13 for participants receiving IP for 48 weeks.

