- c V11 and V12 do not occur for participants with a final dose at or before V10. Participants resume the visit schedule with V13 (Week 48). V14 may be optional for some participants, as determined by the sponsor.
- d Follow-up visits are not required if the participant meets release requirements determined by the sponsor.
- e For Part B ED visit, collect florbetapir F 18 PET scan only if a florbetapir F 18 PET scan has not yet been performed and participant has received at least 3 doses of donanemab.
- f Unscheduled lab tests may be performed at the discretion of the investigator. Collect labs prior to administration of IP, unless otherwise noted.
- g Perform the flortaucipir F 18 and florbetapir F 18 PET scans  $\geq$ 16 hours apart from each other.

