#### **4.1.3. Part B: Open-Label Donanemab**

Part B is an open-label donanemab phase beginning at Visit 1. Participants should participate in, at a minimum, Pair 1 of Part A before starting Part B.

At Visit 1, appointments should be made for all remaining visits and should be scheduled as close as possible to the target date, relative to Visit 1.

Assessments and procedures will be performed as indicated in the SoA (Section 1.3). Procedures for some visits may take more than 1 day.

The study investigator and site clinical study team will not have access to florbetapir F 18 PET results during the study to increase objectivity of cognitive assessments.

Participants who meet entry criteria for Part B will be enrolled to receive up to 48 weeks of treatment with donanemab IV Q4W.

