## **10.5. Appendix 5: Florbetapir F 18 Amyloid PET Imaging**

Florbetapir F 18 PET scans will be performed as part of the study as indicated in the SoA (Section 1.3).

Site investigators, participants, and study partners will not be informed of scan results obtained. Any significant findings that may be of potential medical concern will be provided for appropriate follow-up.

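### If the Week 36 dosing stop is based on PET, whether dosing continues lets sites, participants and study partners infer the PET category before the later Part B cognitive and functional ratings

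*Protocol*

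**What the plan says.** **The stop.** Protocol section 4.1 (and the synopsis) gives two dosing durations in Part B: "Participants may receive donanemab through Week 36 or Week 48". The sponsor defines the criteria for the earlier stop. These "may be based on results of the participant's florbetapir F 18 PET scan at Week 36" "or results from external studies such as Study AACG". The documents do not say which basis will be used.

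**Withholding of PET results.** Section 4.1.3 says that the investigator and site clinical team "will not have access to florbetapir F 18 PET results during the study to increase objectivity of cognitive assessments". Appendix 5 (section 10.5) goes wider but gives no purpose: "Site investigators, participants, and study partners will not be informed of scan results obtained".

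**What the stop looks like at the site.** The Schedule of Activities (section 1.3) says of the infusions: "Only administer IP at V11, V12, and V13 for participants receiving IP for 48 weeks". Its footnote c says of the visits: "V11 and V12 do not occur for participants with a final dose at or before V10". No dummy infusion is described, and section 6.3 confirms that Part B is open label.

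**Rater masking.** Section 8.1.2 masks the CDR rater to adverse events. It does not mention masking any rater to dosing status or visit attendance.

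**The concern.** The protocol withholds PET results in an open-label phase for a stated reason: to help keep the cognitive ratings objective. It also allows the same participant-level scan to decide whether infusions continue after V10. Under that option the scan value stays hidden but its consequence does not. Someone who knows the criterion and sees that infusions have stopped, or have continued, can infer the category.

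The ratings most exposed are those that depend on a person's report or judgement. The study partner answers the ADCS-ADL, and the CDR is scored by a clinician after interviewing partner and participant. Knowing that everyone receives donanemab is common to all of Part B. An inferred amyloid category differs between participants, so the expectation it creates can differ too. The affected ratings include Week 72, where the secondary clinical endpoints end. Protocol section 9.4.3 also allows progression to be compared with what would be expected without treatment, if numbers are adequate.

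**Working it through.** The plan states no power or error-rate figure on this point. The check is a timeline, a count of visits and a comparison of sections.

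**1. When dosing status becomes visible** (Schedule of Activities)
- The florbetapir PET is due at Week 36 ± 14 days, so between Week 34 and Week 38.
- V11 is at Week 40 ± 7 days, so between Week 39 and Week 41. By then the participant has either attended and been infused or has no visit.
- V13, the next rating visit, is at Week 48 ± 7 days, so between Week 47 and Week 49.
- Gap between visible status and the next rating: 47 − 41 = 6 weeks at the shortest, 48 − 40 = 8 weeks nominally, 49 − 39 = 10 weeks at the longest.

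**2. How many ratings follow**
- The ADAS-Cog13, ADCS-ADL, CDR-SB and MMSE are scheduled after baseline at V4, V7, V10, V13, V14 and V15 (Weeks 12, 24, 36, 48, 60 and 72). Three of these six come after V10.
- Footnote c makes V14 optional for some participants. Without it the count is 2 of 5.
- V801 and V802 (Weeks 84 and 96) bring the maximum to 5 of 8. Footnote d says they are not required if the sponsor's release requirements are met.

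**3. Who can infer what, under each basis for the stop**

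| Basis of the Week 36 stop | What continued or stopped dosing shows |
|---|---|
| Participant's own PET | Which side of the criterion the scan fell on; not the value |
| Uniform rule from external results | Nothing about the individual scan |
| ARIA, adverse event, request or other reason in section 7.1 | Nothing about the individual scan |

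The third row does little to hide the first. Such stops are generally decided by, or known to, the investigator, who can tell them from a scheduled stop.

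**4. Whether raters would notice**
- The rater table in section 8.1.2 places the C-SSRS with the psychometric rater, and the schedule has it at every Part B visit. That rater would see directly whether V11 and V12 take place.
- The global rater gives the ADCS-ADL and CDR. Neither is scheduled at V11 or V12, so this rater need not know, but nothing in the protocol prevents it.
- Later procedures also differ. A random PK sample is taken at V13 if no dose is given, and the ECG and safety laboratory tests at V14 are not required for those who finished at V10.

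**5. Size**

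For any one scale, bias in the Week 72 mean = p × d(stop) + (1 − p) × d(continue). Here p is the share stopped at Week 36 on the criterion, and each d is the average shift in score from inferring the category. The documents give neither the criterion, nor p, nor either d. The scales also run over different ranges (CDR-SB 0 to 18, MMSE 0 to 30, ADCS-ADL 0 to 78, ADAS-Cog13 0 to 85), so one shift in points would not mean the same thing on each. No figure can be derived.

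**The case against.** The strongest reply is that nothing is literally contradicted. The PET basis is only permitted, no scan result is released, and section 4.1.3 speaks of increasing objectivity, not guaranteeing it. Part B is single-arm and open label, its primary objective is safety, and section 9.1 states no hypotheses for it. Expectation can affect every rating from the first infusion, and SAP 7.5 only summarises the efficacy scales. There are also partial safeguards: sections 8.1.2 and following separate the ADAS-Cog13/MMSE rater from the ADCS-ADL/CDR rater and provide audio recording for central monitoring. The ADAS-Cog13 and MMSE are tests performed by the participant and less open to partner expectation.

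Most of this stands, and it rules out several stronger readings:
- **That the protocol discloses PET results.** A reader might infer this, but at most a category can be inferred, and only under the PET-based option.
- **That the objectivity safeguard was promised for participants and partners too.** Section 4.1.3 gives that purpose for the site team only. Section 10.5 covers participants and partners without giving a purpose.
- **That a planned comparison by clearance or dosing duration is biased.** None is planned. The section 9.4.3 model has no term for either, and SAP 7.7 plans no subgroup analyses for the safety population.
- **That the bias can be put in points.** It would rest wholly on assumed inputs.

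The reply does not dispose of the narrower point. The protocol chose to withhold PET results although dosing is open, and under one of its own options that measure works only in part after V10.

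**Conclusion.** The point holds conditionally. If the sponsor uses the PET-based criterion, and those involved know that it does, continued or stopped dosing partly defeats the purpose given in section 4.1.3 and the non-disclosure in section 10.5. The affected ratings are V13, V14 where done and V15 within the Week 72 secondary endpoints, and V801 and V802 where done. Week 36 is the last rating fully protected, provided the decision is not communicated before the V10 ratings; the documents do not say when it is. The PET window opens at Week 34, so earlier communication is possible.

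The consequence is limited to the objectivity of secondary clinical ratings, mainly CDR-SB and ADCS-ADL, and of the iADRS through its functional component. The Part B safety objective is not put in doubt. The direction and size of any shift are unknown. The passages should be reconciled; this review takes no view on the dosing rule.

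**What to change.** Reconcile sections 4.1, 4.1.3 and 10.5 without changing the dosing rule.

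1. **Section 8.1.2.** Extend the existing masking of the CDR rater. From V10, the global rater (CDR and ADCS-ADL) is not told whether the participant is dosed at V11 to V13 or attended V11 and V12, and study partners are asked not to discuss it with that rater.
2. **Sections 4.1.3 and 10.5.** Keep the statement that scan results are withheld, since that remains true after V10. Add that, if a PET-based criterion is used, dosing status after V10 may indirectly indicate the PET category, so Week 36 is the last fully protected rating. State in section 4.1 which basis was used once it is set, and that the decision is communicated only after the V10 ratings.
3. **SAP 7.5.** Add one sentence that ratings after Week 36 are to be interpreted with this in mind.

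The cost is a short rater instruction and some wording; separate psychometric and global raters already exist. There are limits. Partner knowledge is only partly controlled. The psychometric rater cannot readily be masked while also giving the C-SSRS at every visit; that would need other staff. Small sites must take care to keep dosing status from the global rater. If masking proves impractical, items 2 and 3 still make the documents accurate.
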